## 8.1.10 Depression, Suicidal Ideation or Attempt

Participants living with HIV-1 infection may occasionally present with symptoms of depression and/or suicidal ideation or behavior. Participants who experience symptoms of depression and/or suicidal ideation or behavior, or report delusions and inappropriate behavior, regardless of relationship to study drug, should be managed and re-evaluated according to standard of care

practice at the site, or more frequently, or referred for specialist evaluation and treatment, at the discretion of the site investigator. Refer to the IMPAACT 2036 MOP for additional guidance regarding establishing a baseline screening assessment for depression. Participants reporting new symptoms of depression will be asked to contact the study IoR or designee immediately if symptoms of severe acute depression (including suicidal ideation/attempts) develop. All sites should have a plan in place for managing possible risks for suicide related events.

- **Grades 1 or 2:** Manage per site standard of care and SOPs.
- **Grade 3 or higher:** Manage per site standard of care and SOPs and consult the CMC within 24 hours.

## 8.1.11 Management of QTc Prolongation

See Section 6.12 for the specifications requiring repeat ECG readings. If any one of the repeated readings confirm a Grade 3 or Grade 4 QTc Prolongation Interval (using the Fridericia formula provided in the IMPAACT 2036 MOP), temporarily hold study product and assess participant for concomitant medications known to cause prolonged QT or Torsades de Pointes. Study product may be resumed in consultation with the CMC, and if the prolonged QTc is assessed as not related to study drug. If the prolonged QTc is assessed as related, or no other likely cause identified, permanently discontinue study product.

For any other abnormality or irregularity reported by the automated read during follow-up that is considered clinically significant by the qualified site clinician, a cardiologist should be consulted, and the CMC notified.

# 8.2 Management of Pregnancy

Section 6.13 provides details on pregnancy testing, contraceptive counseling, and contraceptive use guidance, including the effective contraception methods allowed in the study.

A pregnancy test result must be obtained from a specimen collected on the same day as and prior to administration of study product for participants of childbearing potential. A temporary product hold should be put into place and the CMC should be notified immediately and no later than 24 hours following receipt of a positive pregnancy test result. A confirmatory pregnancy test should be conducted as soon as possible and within 48 hours. Any participant still on oral lead-in when a pregnancy is confirmed will be permanently discontinued from study product. For participants receiving injectable study products, the CMC will make a determination about continued product use weighing the benefit/risk ratio for the participant and fetus and will communicate their decision to the site team within 3 business days of the original notification. Following the CMC recommendation, and in consultation with the IoR or designee, the participant and parent/legal guardian (as applicable) will make a decision about ongoing treatment options during pregnancy. See Section 5.1.3 and Section 8.4 for more information on oral bridging and temporary product holds and Section 13.3.2 for parental permission, informed assent, and informed consent requirements.

Participants who permanently discontinue study product use due to pregnancy will be followed per the LSFU visit schedule based on their confirmed positive pregnancy test result; see Section 6.6. In these circumstances, the choice of cART regimen is at the site investigator's discretion and in accordance with the local standard of care and available resistance profiles, and appropriate for use in pregnancy. Sites should actively refer pregnant participants to antenatal standard of care, and to engage in antenatal care as early in the pregnancy as possible.

Pregnancy test results and pregnancy outcomes will be ascertained and entered into eCRFs for all pregnant participants. Pregnancy outcomes should be ascertained based on medical records; when medical records are unavailable, maternal report may be used. Pregnancy related complications and diagnoses, and outcomes will be reported as adverse events and EAEs as outlined in the protocol in Section 7.

Participants who are pregnant will remain on study through delivery or other pregnancy outcome; see Section 6.8. If the site becomes aware of a pregnancy complication occurring after the participant has exited the study, and the pregnancy complication is assessed as related to study drug, the CMC should be notified immediately and no later than three business days after site awareness.

Study sites will also be encouraged to prospectively register the participant's pregnancy in the Antiretroviral Pregnancy Registry: http://www.apregistry.com/ (in US: [name]).

## 8.3 Monitoring and Management of HIV-1 Viral Load

#### Monitoring

HIV-1 RNA (viral load) will be monitored closely with frequent testing as specified in the Schedules of Evaluations in Appendix I. All HIV-1 RNA assays must be performed in a CLIA-certified or equivalent (US sites) or VQA-certified (non-US) laboratory using the testing platform specified in the LPC.

Site investigators should review the results of each test as well as trends over time and consult with the CMC regarding any individual test results or trends of concern. Viral load results should be provided to participants and may be used to guide adherence counseling.

#### Definition and Confirmation of Virologic Failure

Virologic failure is defined as two successive plasma HIV-1 RNA test results ≥200 copies/mL, from separate specimens collected at least two weeks apart.

Any participant with a plasma HIV-1 RNA level ≥200 copies/mL after enrollment should be recalled to the clinic for completion of the Confirmation of Virologic Failure visit. Refer to Section 6.7 for details regarding this visit.

#### Definition and Management of Confirmed Virologic Failure

The CMC should be consulted regarding any participant with confirmed virologic failure. All participants with confirmed virologic failure will be permanently discontinued from study product. Refer to Section 8.5 for participant management regarding permanent discontinuation of study product. Participants with confirmed virologic failure during the oral lead-in phase will be terminated from the study and will complete an Early Termination visit 28 days after last oral study product use. Participants with confirmed virologic failure during the injection phase or during the course of the LSFU visit schedule will be followed per the LSFU visit schedule; see Section 6.6.

HIV-1 genotypic and phenotypic resistance samples will be processed and stored per Section 6.16.2 and the LPC. Upon confirmation of virologic failure, shipping and testing of resistance samples will be performed, per Section 6.16 and the LPC. These resistance test results will be reviewed by the site investigator of record, or designee, and used to inform a recommended cART regimen, in consultation with the CMC. Participants should resume the recommended non-study provided oral cART as soon as possible and within 4 weeks.

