# 6.6 Long-Term Safety and Washout PK Follow-Up (LSFU) Visits

Participants who prematurely and permanently discontinue injectable study product, or participants who discontinue study product use (either oral or injectable study product) due to pregnancy, will be followed for an additional 48 weeks to assess long-term safety and washout PK of the study products. Additionally, participants who receive their injections at their final scheduled follow-up visit (Week 72 for Cohort 1, Week 48 for Cohort 2a, and Week 44 for Cohort 2b) but do not wish to continue the CAB LA + RPV LA regimen outside of the study will resume (non-study provided) ART and enter into the LSFU visit schedule. Participants will resume (non-study provided) oral cART as soon as possible, and within 4 weeks, or 8 weeks (±7 days), of discontinuing study product depending on the study product dosing regimen which was discontinued (i.e., O4W or O8W dosing regimen). The LSFU visits will be scheduled approximately 4, 8, 24, 36, and 48 weeks after the last injection, after which participants will exit the study. Participants who permanently discontinue study product (either oral or injectable study product) due to pregnancy will be followed for 48 weeks, based on the date of the positive confirmatory pregnancy test result. For participants who become pregnant during LSFU visits, the LSFU visits will continue as scheduled and not restart. All LSFU visit procedures will be conducted, with the exception that pregnancy testing will not be required for participants who are currently pregnant. See Section 8.2 for further details on management of pregnant participants and pregnancy outcome.

During LSFU, a single random PK sample will be collected at each visit as shown in the procedural tables below.

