# 6.7 Confirmation of Virologic Failure Visit

Any participant with a plasma HIV-1 RNA level ≥200 copies/mL after enrollment should be recalled to the clinic for completion of the Confirmation of Virologic Failure visit for confirmatory testing 2-4 weeks after specimen collection for the initial test. Scheduling of this visit within the timeframe specified should also be in consideration of potential causes for virologic failure such as intercurrent illness, recent immunizations, inadequate adherence, interruptions of study product, or other extenuating circumstances. For participants receiving injectable study product, confirmatory test results should ideally be obtained and reviewed prior to the next scheduled administration of injectable study product. While injection study visits for these participants may be delayed within the respective target visit window, injectable study product must not be withheld for pending confirmatory testing or results.

Confirmation of Virologic Failure visit procedures may be combined with regularly scheduled visit procedures if they are performed within the target window of a regularly scheduled visit. In addition to the protocol-specific procedures listed in this section, study staff may complete other tasks and assessments consistent with local standards of care and site SOPs.

The viral load results from the Confirmation of Virologic Failure visit will determine whether the participant has met the criteria of virologic failure for the study (See Section 8.3 for the definition and management of virologic failure). Viral load results should be provided to participants and may be used to guide adherence counseling. See Section 6.14 for additional details on adherence counseling.

Confirmation	on of Virolo	ogic Failure Visit Procedures	
Behavioral and		Provide contraceptive counseling*^	
Counseling		Provide adherence counseling*	
Clinical		Obtain interval medical and medications history	
		Perform targeted physical exam	
		Identify/review/update adverse events	
		Perform additional evaluations per Section 8.3 and/or if clinically indicated	
		(consult CMC if indicated)	
Laboratory	y Blood Collect blood for:		
		• HIV-1 RNA	
		Plasma for genotypic and phenotypic resistance testing	
		PK evaluation: Single sample	
Blood or		Pregnancy test^	
Urine			

\*If indicated

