## 8.5 Criteria for Premature Permanent Discontinuation of Study Product

See Section 6.6 for guidance regarding participant management in the event of early termination or withdrawal from study participation. Administration of study product will be permanently discontinued in the following circumstances:

- Participant intention to discontinue study product or study follow-up
- During the oral lead-in phase, sustained non-adherence to oral regimen that, in the opinion of the investigator and in consultation with the CMC, warrants early study product discontinuation.
- Sustained non-adherence to injection visit schedule that, in the opinion of the investigator and in consultation with the CMC, warrants early study product discontinuation (per IoR discretion, a temporary product hold may be initially implemented; see Section 8.5).
- The participant requires treatment with prohibited medications (see Section 5.7).
- During the oral lead-in phase, confirmed pregnancy; see Section 8.4 for product management during injectable phase in the context of a positive pregnancy test.

- Participants of childbearing potential who are engaging in sexual activity that could lead to
  pregnancy refuse use of an effective contraceptive method without an intention to
  resume/initiate.
- The participant experiences an adverse event that requires discontinuation as defined in Section 8.1.
- Virologic failure as described in Section 8.3.
- The site investigator determines that further administration of study product would be detrimental to the participant's health or well-being.
- New data become available that indicate study products should be discontinued as determined by the CMC.

Participants who permanently discontinue study product should resume (non-study provided) cART as follows:

- Cohort 1 and Cohort 2a participants during the oral lead-in phase: as soon as possible and within 4 weeks of their last oral study product use.
- All participants during injectable phase and on a Q4W dosing regimen: within 4 weeks of their last study product injection.
- All participants during injectable phase and on a Q8W dosing regimen: at 8 weeks ( $\pm 7$  days) after their last study product injections.

Participants who permanently discontinue oral study product will be instructed to return all oral study products to the site clinic as soon as possible.

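### If Q8W dosing is adopted, Sections 8.3 and 8.5 give a child with confirmed virologic failure conflicting dates for restarting cART, and no text says which prevails

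*Protocol*

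**What the plan says.** Section 8.3 (Definition and Management of Confirmed Virologic Failure) requires permanent discontinuation of study product and sets the return to outside therapy: "Participants should resume the recommended non-study provided oral cART as soon as possible and within 4 weeks". It does not distinguish Q4W from Q8W and gives no start point for the 4 weeks. It also sends the site elsewhere: "Refer to Section 8.5 for participant management regarding permanent discontinuation of study product". Failures in the injection phase are then followed under Section 6.6.

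Section 8.5 includes this among its discontinuation reasons: "Virologic failure as described in Section 8.3". It then sets restart timing by regimen. For Q4W: "All participants during injectable phase and on a Q4W dosing regimen: within 4 weeks of their last study product injection". For Q8W: "All participants during injectable phase and on a Q8W dosing regimen: at 8 weeks", with a tolerance of 7 days either side, counted from the last injections. Neither bullet makes an exception for virologic failure.

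Section 6.6 repeats the split by regimen, with restart "as soon as possible, and within 4 weeks, or 8 weeks (±7 days), of discontinuing study product", also without an exception.

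Section 6.7 calls the child back "for confirmatory testing 2-4 weeks after specimen collection for the initial test" and adds that "injectable study product must not be withheld for pending confirmatory testing or results".

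**The concern.** The Q4W bullet of Section 8.5 is an upper limit, so an early restart complies with both it and 8.3. The Q8W bullet is a window with an earliest day. Its 49–63 days are the same interval in which Appendix II places the next regular Q8W injection. That timing suits a suppressed child being handed over when the next dose would fall due. It does not suit a child whose regimen has failed.

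A site applying the Q8W bullet as written would hold back effective therapy from a viraemic child, while a site applying 8.3 would not. At stake are the child's safety and consistent conduct across sites. Section 1.2.5.1 warns of resistance to either drug after injections stop. It does not quantify any added risk from a delayed restart in a child who is already failing, and none is claimed here.

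**Working it through.** There is no statistical figure to reproduce; the check compares the texts and counts days.

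**Inputs**
- Section 8.5, Q8W: 56 ± 7 gives Days 49–63 after the last injection.
- Section 6.7: confirmatory draw D is 14–28 days after the failing sample.
- Section 6.1.2: on Q8W, scheduled laboratory tests are done only at injection visits, so the failing sample and an injection share Day 0.
- Appendix II, Q8W: the next regular injection is at Days 49–63 (49–59 for Week 16, counted from Week 8). The Week 8 injection, W, is 21–31 days after Week 4b.
- Result turnaround T is not stated in the protocol. Assumed range: 0–14 days. Confirmation is C = D + T.

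**Regular Q8W visit** (Day 0 is both the failing sample and the last injection)
- No further injection is due before Day 49, so Day 0 remains the last injection.
- Draw to opening of the 8.5 window: 49 − 28 = 21 to 49 − 14 = 35 days. Draw to closing: 63 − 28 = 35 to 63 − 14 = 49 days.
- C runs from 14 + 0 = 14 to 28 + 14 = 42, so the window opens 49 − 42 = 7 to 49 − 14 = 35 days after confirmation.

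Whether one date can satisfy both outer limits depends on when the 4 weeks in 8.3 start:
- *From the last injection:* the limit is Day 28, which is 49 − 28 = 21 days before the window opens. The limits never overlap. On this reading the limit could also pass before failure is confirmed, since C can be as late as Day 42.
- *From confirmation:* the limit is C + 28. A shared date needs C + 28 ≥ 49, so C ≥ 21. For C = 14–20 the limit falls on Days 42–48 and there is no shared date. For C = 21 or later the outer limits overlap.

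On either reading, an instruction to restart as soon as possible conflicts with an earliest date of Day 49.

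**Initiation case** (failing sample at Week 4b on Day 0; Week 8 injection given while confirmation is pending, as Section 6.7 requires)
- The last injection is now W, so the 8.5 window opens at W + 49: Day 70 (W = 21) to Day 80 (W = 31).
- The result must still be outstanding at W, so W − D ≤ T ≤ 14.
- Shortest interval from draw to opening: W = 21, D = 28 gives 70 − 28 = 42 days.
- Longest: W = 31 needs D ≥ 31 − 14 = 17, giving 80 − 17 = 63 days.
- With 8.3 counted from confirmation, a shared date needs C + 28 ≥ W + 49, so C ≥ W + 21. Since C ≤ 42 and W ≥ 21, this is met only at W = 21, C = 42.

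These counts do not cover Cohort 2b Week 2 samples or failures found during long-term follow-up.

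**The case against.** The strongest reply is that Section 8.3 is the only text written for confirmed virologic failure. The 8.5 bullet is a general rule for all discontinuations, and its virologic-failure item points back to 8.3. Reading the specific rule over the general one is ordinary practice. Section 8.3 also calls for CMC consultation on every confirmed failure and on the choice of cART, so a site should not be applying the 8.5 bullet alone. Section 6.6 puts promptness first, which makes its 8 weeks look like an outer limit. Q8W applies only if it is adopted.

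All of this lowers the practical risk and should be acknowledged. It does not settle the text. Nothing states that 8.3 prevails, 8.3 itself refers the reader to 8.5, and the 8.5 bullet covers all injection-phase participants on Q8W. The consultation requirement does not say which restart date governs.

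Two stronger readings are tempting. A reader might infer that the rules can never both be met. That holds only for a clock starting at the last injection, which 8.3 does not state. Counted from confirmation after a regular visit, the outer limits fail to overlap only for Days 14–20. A reader might also take 80 − 14 = 66 days as the longest interval in the initiation case. That pairs a Day 14 draw with a result still pending on Day 31, a turnaround of at least 17 days. Within the assumed 14 days the maximum is 63.

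**Conclusion.** The inconsistency is real and limited to Q8W dosing. The part that rests on no assumption is the clash between prompt restart in 8.3 and an earliest date of Day 49 in 8.5. The extent to which the outer limits also clash depends on an unstated start point. Counting from confirmation is the natural reading in context, but it remains an inference. The intervals measured from confirmation, and the 63-day maximum, also rest on the assumed 0–14 day turnaround.

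The documents do not support inferring biased results: the point concerns participant management, and no safety, PK or resistance estimand changes. Few children are likely to be affected. It still merits correction, because one stated rule, followed literally, delays therapy in a child with confirmed viraemia.

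**What to change.** Add to the Q8W bullet of Section 8.5, and mirror in Section 6.6: *except for confirmed virologic failure, where cART is resumed per Section 8.3*. In Section 8.3, state that the 4 weeks run from confirmation of virologic failure.

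Keep the promptness wording in 8.3 as the operative instruction. With a 14-day turnaround, the 4-week limit can fall as late as Day 42 + 28 = 70 after the failing sample, so the outer limit alone would not guarantee an earlier restart than 8.5 does now.

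The cost is one line in each of 8.5 and 6.6 and a start point in 8.3, by clarification memo or at the next amendment. Sample size, visits and analyses are unaffected.

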## 8.4 Deferring Study Product and Criteria for Temporary Hold of Study Product

At each study product administration time point, the site investigator or designee must confirm participant eligibility to receive study product (see Section 6.8). Study product administration must be deferred consistent with the guidance provided in Section 8.4.

For any other significant medical condition that, in the opinion of the investigator, would make it unsafe to administer study product or make it difficult to assess for subsequent study drug related adverse events, if present on the scheduled day of study product administration, administration must be deferred, and the CMC should be consulted on next steps and continued study product management.

For all temporary holds, both study products should be held, and the CMC should be consulted as soon as possible and within 48 hours; the CMC may recommend resuming a (non-study provided) cART regimen in these situations. For participants resuming a cART regimen for the duration of a temporary study product hold, site staff should provide the participant and the participant's parent or guardian with referrals to non-study sources of treatment for the participant, as applicable. See the IMPAACT 2036 MOP for operational consideration and guidance.

Study product will be temporarily held from a participant for any of the following reasons:

- Study product management per Sections 8.1 through 8.4.
- Report of use of prohibited concomitant medications (See Section 5.7). Study product use may
  resume upon consultation with the CMC and when the participant reports that he/she is no
  longer taking the prohibited medication, provided other reasons for temporary study product
  hold/permanent discontinuation do not apply. The CMC should be consulted in all cases of a
  participant reporting taking a prohibited concomitant medication during the course of the study.
- The participant is unable or unwilling to comply with required study procedures, such as protocol-required laboratory assessments or injectable study product visits, or otherwise might be put at undue risk to their safety and well-being by continuing study product use, according to the judgment of the site investigator. The site investigator must consult the CMC on all temporary study product holds instituted for this reason, for further guidance on resuming study product use, continuing the temporary hold, or progressing to permanent discontinuation.

